**Eligibility Criteria:** Inclusion criteria: All caregivers of Veterans with a primary diagnosis of stroke are eligible for participation if they meet the following criteria: 1) are the primary caregiver and provide the majority of care for a Veteran who has a primary diagnosis of stroke (ICD10 codes for stroke: 160.0-169.998) and who has at least one activity of daily living (ADL) deficit or a new or worsening cognitive or physical functioning problem, 2) have internet and email access and ability, 3) are reachable by cell or home phone, 4) read English at the sixth grade reading level or better, 5) score 1 or greater on the Perceived Stress Scale and 6) plan to be ultimately discharged to home or have been discharged home within the preceding 4 months 7) agree to random assignment to the intervention or usual care group.

The research staff will use a checklist for caregiver enrollment to determine the caregivers' eligibility. The research staff will determine whether the Veteran has a primary diagnosis of stroke by reviewing the Veterans' CPRS health record and by conferring with the clinical staff. Caregiver status and responsibilities will be determined by caregiver self-report. We will determine the Veterans' ADL deficits by asking caregivers which ADL deficits their Veteran has on the Barthel Index. Reading level will be indicated by the Brief Health Literacy Level screening tool. Internet and email access and ability will be determined by caregiver self-report.

Exclusion criteria: We will exclude caregivers of Veterans who are terminally ill, who are prisoners, who fail to meet one or more of the inclusion criteria, and whose Veterans have a life expectancy of less than 6 months. We will also exclude professional caregivers who had no preexisting relationship to the Veteran. Caregivers who are enrolled in or have completed similar caregiver support programs will be excluded at PI discretion. Service use will be determined by reviewing the CPRS records. We will confer with the in-patient

staff and with our clinical team members (MDs, RNs) to approximate life expectancy. The study personnel will terminate the caregiver participation if the Veteran dies during the study.

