Rationale for Study Sample Size: The sample will consist of 240 caregivers. Assuming a standard deviation of 8.2, 84 subjects per group would achieve 80% power to detect a mean intervention effect size of 3.5 on depression at a 5% significance level. The sample size of 120 per group (i.e., intervention group, usual care group) was selected to account for the occurrence of a (30%) dropout rate. The 30% drop-out rate is a conservative estimate of attrition and is based on previous caregiver problem-solving intervention studies in the literature and on the attrition rates found in the internet intervention studies of our consultants, Drs. [name] and [name]. The expected effect size and variability was deemed reasonable based on a number of sources. In a study of caregivers of Alzheimer's patients, the investigative team described large changes pre- and post-treatment in a clinical setting, with depression from time of admission to 4 weeks post decreasing 20 points for "recovered" patients and 12 points for "still ill" patients. In a study of a telephone intervention to family caregivers of stroke caregivers, found an estimated 1 month treatment effect of 3.1.

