## **Randomization:**

The proposed study will use a two-group randomized design with 3 assessment points (baseline, approximately 11 weeks, and approximately 19 weeks). Following baseline assessments, the participant will be randomly assigned to one of the two study groups (Intervention or Usual Care). The Pocock-Simon covariate adaptive randomization procedure will be used so that there will be approximately equal number of subjects assigned to the two groups within each covariate level (depressed or not and high or low ADL) and within each study site. The statistician will develop the randomization scheme and share it with the project coordinator and a research staff member at each site. When a caregiver is enrolled in the study, this staff member at site will obtain the group assignment for that caregiver from the randomization system.

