## **Data Analysis:**

Hypothesis #1 (primary): Stroke caregivers who receive the intervention will have less depressive symptoms at approximately 11 and 19 weeks compared to stroke caregivers in the usual care group. Our primary endpoint is the caregiver depressive score. The focus of the primary analysis will be to examine the effect of the intervention based on "intention to treat." Data from all the participants will be part of the primary analyses regardless of actual number of completed in-home sessions. Thus, we are examining the effectiveness of the intervention taking into account real world compliance factors. As an exploratory study element, we will assess compliance and attempt to determine its effect on study results.

For the primary analysis, the general linear mixed model for repeated measures will be used to model the follow-up depression times (approximately 11 and 19 weeks after baseline data collection), adjusted for site and baseline scores as fixed effects. Since the Tampa site has a standardized, discharge planning process that involves Veteran education while the other sites have no discharge planning process, there may be different responses due to usual care between the Tampa versus other sites. Thus, we will first explore whether or not there is a differential treatment effect at the Tampa site by fitting a full model that allows for Tampa to have a differential time and group effect for each time point. Let  $y_{ij}$  be the depression score for person i at time j, then Full fixed effects model will be:

$$E(y_{ij}) = \beta_0 + \beta_1 Baseline_i + \beta_2 Tampa_i + \Sigma_s \beta_{3s} I(Site_i = s) + \beta_4 Time_{ij} + \beta_5 Group_i + \beta_6 Group_i *Time_{ij} + \beta_7 Tampa_i *Time_{ij} + \beta_8 Tampa_i *Group_i + \beta_9 Tampa_i *Group_i *Time_{ij}$$

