with covariates for baseline depression and time since discharge (*Baseline*), site (e.g., *Tampa*=1 if Tampa, 0 otherwise; and  $\beta_{3s}$  represent effects of sites compared to reference site Gainesville), time (*Time*=0 for 11 weeks, 1 for 19 weeks), and group (0 if active control, 1 if intervention). Of primary interest is the estimated within-site intervention effect at approximately 11 weeks after baseline data collection, controlling for baseline and stratifying by site. The initial test will be the test of  $\beta_8$ +  $\beta_9$ =0, which tests whether the Tampa site has a differential group effect compared to the other sites at approximately 11 weeks after baseline data collection. If a site difference in treatment effect is found, then results will be conditional on Tampa or Miami/Gainesville. In this case, the primary tests of interest will be the estimated within-site intervention effect at approximately 11 weeks after baseline data collection, controlling for baseline and stratifying by site. In the model above, this corresponds to the test of  $\beta_5$  =0 for other sites and  $\beta_5$  + $\beta_8$ =0 for Tampa. If no difference is found in our initial interaction test, we will assume that the Tampa site does not have a differential treatment effect and the interaction will be removed from the model. The new fixed effect portion of the model will simplify to the Reduced model:

$$E(y_{ij}) = \beta_0 + \beta_1 Baseline_i + \beta_2 Tampa_i + \Sigma_s \beta_{3s} I(Site_i = s) + \beta_4 Time_{ij} + \beta_5 Group_i + \beta_6 Group_i *Time_{ij}$$

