Of primary interest is the estimated within-site intervention effect at approximately 11 weeks after baseline data collection, controlling for baseline covariates and stratifying by site. In the model above, this is the test of  $\beta_5$  =0. In order to control for possible chance sample imbalances resulting from randomization, the model will include covariates for baseline prognostic factors (e.g., discharge from hospital, community living center, or rehabilitation facility; caregivers' relationship to Veteran; number of previous strokes among Veterans, etc.), deemed to have significant relationships with response and groupwise imbalances. Thus, analyses will be able to compare the groups on the measure of interest while controlling for these factors. As a supplemental analysis we will assess long term intervention effects at the approximately 19 week after baseline data collection time point. In the Full model above, this is the test of  $\beta_6$  =0 for other sites, and  $\beta_6$ +  $\beta_9$ =0 for Tampa. In the reduced model, this is simply the test of  $\beta_6$  =0. All tests will be performed at the  $\alpha$ =0.05 significance level. The correlation among observations from the same person will be accounted for through the inclusion of a random person effect into the mixed model analysis.

Hypotheses #2 (secondary): (2a) Stroke caregivers who receive the intervention will have superior outcomes (i.e., less burden, less stress, greater self-efficacy, perceive greater positive aspects of

caregiving, better HRQOL, and greater satisfaction with care) at approximately 11 and 19 weeks after baseline data collection than caregivers in the usual care group.

The analysis plan for Hypothesis 2 will closely follow the plan outlined above for Hypothesis 1 for each secondary outcome of interest.

Hypotheses #3 (secondary): Veterans whose caregivers receive the intervention will have better functional abilities at approximately 11 and 19 weeks after baseline data collection and less healthcare utilization at approximately 11 and 19 weeks after baseline data collection compared to Veterans whose caregivers are in the usual care group.

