Since the Barthel Index score can be treated as continuous, the analysis plan follows exactly as above in Hypothesis 1. Since the Veteran healthcare utilization measures are count data, the models will be somewhat different. There will be no baseline covariates added to the model, as they are not applicable to the count measures. Analyses will be conducted for the period following baseline data collection to approximately 11 weeks and 19 weeks after baseline data collection. Generalized linear models for count data (such as Poisson or negative binomial regression models, depending on the presence or absence of over-dispersion) will be employed to determine the group effects on healthcare utilization. As before, the site type will be included in the full model and possible site differences will be accounted for. Log link functions will be employed on the count data to create the correct distributional data forms. As before, in order to control for possible sample imbalances resulting from randomization, all models will include covariates for prognostic factors deemed to have significant relationships with response and significant groupwise imbalances. Thus, analyses will be able to compare the groups on the measures of interest while controlling for these factors.

Handling of Missing Data: We should not have a problem with missing data as our data will be collected inperson or over the telephone. Our data collectors will receive extensive training on interviewing and how to politely encourage participants to answer all questions on research instruments. In the event of drop-outs, the missingness mechanism will be explored. If the assumption of Missing Completely at Random (MCAR) or the common assumption of Missing at Random (MAR) are plausible, then little change to the analysis plan is necessary. The mixed models analysis using direct-likelihood approaches will be unbiased and appropriate. Study efficiency (power) will of course be affected by the smaller amount of available information, thus we have inflated the planned recruitment sample size. If the missingness assumptions are not plausible, then Missing Not at Random (MNAR) techniques will be employed and analysis results will be interpreted with caution.

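### Assignment is balanced on high/low ADL, but the primary model has no ADL term and the covariate rule would almost never add one, at a small cost in power

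*Combined protocol and SAP*

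**What the plan says.** - **Randomization.** Pocock-Simon minimization is to give roughly equal numbers in the two groups "within each covariate level (depressed or not and high or low ADL) and within each study site".
- **Data Analysis, Hypothesis #1, model.** The mixed model for the two follow-up CES-D scores is "adjusted for site and baseline scores as fixed effects", and the equation is described "with covariates for baseline depression and time since discharge". The full and reduced equations also contain Tampa, site, time, group and interaction terms. Neither has an ADL or Barthel term.
- **Data Analysis, Hypothesis #1, extra covariates.** Other baseline prognostic factors are added when "deemed to have significant relationships with response and groupwise imbalances". The examples are discharge facility, relationship to the Veteran and number of previous strokes. The list is left open and does not name ADL.
- **Data Analysis, Hypotheses #3.** The Barthel outcome follows the Hypothesis #1 plan, so it would carry its own baseline value. For the utilization counts, the text first says that baseline covariates do not apply, then says all models will include "covariates for prognostic factors deemed to have significant relationships with response and significant groupwise imbalances".
- **Rationale for Study Sample Size.** "Assuming a standard deviation of 8.2, 84 subjects per group would achieve 80% power" for a "mean intervention effect size of 3.5 on depression at a 5% significance level", with 120 per group enrolled to allow for 30% dropout.

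**The concern.** Three factors steer the allocation, and only two reach the primary analysis: site directly, and depression through the baseline score. No reason is given for dropping the third.

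Balancing a prognostic factor makes the true spread of the treatment estimate smaller. A model that omits the factor leaves its variance in the residual, so the reported standard error does not show that gain. The interval is then wider than it need be and the test mildly conservative.

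The extra-covariate rule does not repair this, because it asks for an imbalance that the allocation method is there to prevent. The rule also has a weakness of its own. A relationship with response can be judged only once outcomes are known, the candidate list is open, and the Hypothesis #1 text gives no cut-off for imbalance. Two analysts could follow the plan and report different primary estimates.

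**Working it through.** **The plan's own figure.** Inputs from the sample-size rationale: difference 3.5, SD 8.2, 84 per group, 5% level (two-sided assumed).

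- SE = 8.2 × √(2/84) = 1.265. Power = Φ(3.5/1.265 − 1.96) = 79.0% (78.5% with the t distribution), close to the stated 80%.
- Solving for 80% power: n = 2 × [8.2 × (1.960 + 0.842)/3.5]² = 86.2 per group.
- 84/0.70 = 120, as stated.

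The calculation takes no credit for covariates and does not say whether 8.2 is a raw or a residual SD.

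**Closed form under perfect ADL balance.** Let R² be the share of the variance left after baseline and site that ADL explains. It is not in the documents, so 3%, 6% and 10% are assumed. The true SE is SE₁ = 1.265 × √(1 − R²) whether or not ADL is in the model. A model without ADL still reports SE₀ = 1.265.

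- SE₀/SE₁ = 1/√(1 − R²) = 1.015, 1.031, 1.054.
- Power with ADL = Φ(3.5/SE₁ − 1.96) = 80.2%, 81.4%, 83.0%.
- Power without ADL = Φ((3.5 − 1.96 × SE₀)/SE₁) = 79.4%, 79.7%, 80.2%.
- Difference before rounding: 0.85, 1.69 and 2.81 points.

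**Simulation under minimization.** There were 59,401 trials in all. Each randomized 240 caregivers on 8 sites, depression and ADL, and 168 completed at random. The analysis was ANCOVA at week 11 with site and baseline. Assumed: biased coin 0.8, 38% depressed, ADL split 50/50.

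| R² for ADL | Model SE without / with ADL (residual SD units) | SE excess | Type I without ADL | Power without / with, residual SD 8.2 | Raw SD 8.2, baseline r=0.5 | Raw SD 8.2, r=0.7 |
|---|---|---|---|---|---|---|
| 3% | 0.1560 / 0.1538 | 1.4% | 4.8% | 77.6 / 78.5 | 88.3 / 88.9 | 96.9 / 97.2 |
| 6% | 0.1560 / 0.1514 | 3.0% | 4.6% | 77.8 / 79.8 | 88.5 / 89.8 | 97.1 / 97.5 |
| 10% | 0.1560 / 0.1481 | 5.3% | 4.3% | 78.1 / 81.4 | 88.8 / 91.0 | 97.2 / 98.0 |

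The loss is 0.9 to 3.3 points if 8.2 is residual and 0.2 to 2.2 points if it is raw (differences taken before rounding). Type I error with ADL in the model is 5.0%. If ADL explains nothing, including it costs about 0.1 point.

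**Weaker association.** At a partial correlation of 0.1 (R² = 1%), the change in SE alone, 1.265 to 1.259, moves power from 79.0% to 79.4%.

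**How often the rule admits ADL.** With random dropout, both conditions were met in 0.04% to 0.07% of trials when imbalance meant p<0.05, and in 1.4% to 2.2% at p<0.20. A separate simulation of 1,500 runs per setting gave 0% to 0.13% and 0.5% to 2.7%.

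**Stress case (assumed).** In the intervention arm, dropout was 40% for low ADL and 20% for high ADL; in control it was 30%. The rule then admits ADL in 2.1% to 3.7% of trials (p<0.05) or 16% to 27% (p<0.20). The estimate without ADL shifts by 0.2 to 0.4 CES-D points; with ADL it shifts by 0.0.

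**The covariate rule by itself.** Six further factors, not minimized, each explain 1% or 3% (assumed). Five readings were compared: no adjustment; imbalance at p<0.05, p<0.10 or p<0.20; standardized difference above 0.1. Any single reading fixed in advance keeps type I error at 4.7% to 5.3%. Reporting the most favourable of the five gives 6.1% (1% each) or 7.1% (3% each). A fixed list of the six has 78.5% or 83.6% power, against 77.5% or 77.7% for the rule at p<0.05.

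**The case against.** The main counter-argument is that this is a precision point of unknown size. The documents give no association between ADL and caregiver CES-D, and a dichotomized factor may add little beyond baseline CES-D and site. The sample size does not rely on covariate adjustment, so there is no shortfall from the stated 80%. If 8.2 is a raw SD, power without ADL is already 88% to 97%. All of that stands, and it limits the point to a small one.

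The rule's stated aim is to correct chance imbalance, so passing over a balanced factor is the rule working as intended. That is fair, and the plan does not contradict itself here. It does confirm that the rule cannot bring ADL into the model.

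The 5% level set for all tests, together with the word significant in the Hypotheses #3 version, suggests p<0.05 for imbalance. That is the natural reading, but neither text gives a cut-off for covariate selection. The 6.1% and 7.1% error rates arise only if the best of several readings is reported, which nothing in the plan proposes. They illustrate the room left open and do not forecast what will happen.

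Three limits on the evidence also stand. The simulations used one time point in completers, not the two-visit mixed model, and omitted time since discharge. No calculation was made for the count models. Barthel is documented at screening ("ADL deficits by asking caregivers which ADL deficits their Veteran has on the Barthel Index"), but the baseline questionnaire list under Data Collection does not name it. High/low ADL must nevertheless be known before assignment, because the allocation uses it.

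**Conclusion.** The concern holds. ADL is a minimization factor, it is absent from the primary model, and the related-and-imbalanced rule would almost never admit it.

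The consequence is conditional and modest. If ADL explains 3% to 10% of the residual variance, the standard error is 1.4% to 5.3% wider than needed, up to about 3 points of power are given up relative to an adjusted model, and type I error falls to between 4.8% and 4.3%. With dropout unrelated to ADL the estimate is unbiased, and if ADL is not prognostic nothing is lost. These sizes rest on the assumed strength of ADL and the assumed allocation settings.

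The outcome-dependent covariate rule is a companion weakness, also minor, and it remains whether or not ADL is prognostic. The change is worth making because it is nearly free.

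**What to change.** - Add ADL as a fixed effect in the full and reduced primary models and in the Hypothesis #2 models, whatever imbalance is observed. Use the high/low factor as recorded in the randomization system, or baseline Barthel. Keep site, baseline CES-D and time since discharge.
- Include the minimization factors (site, baseline depression, ADL) in the utilization count models, and reconcile the two statements there about covariates.
- Replace the rule with a list fixed before outcomes are seen. The plan's own examples would serve: discharge facility, relationship to the Veteran, number of previous strokes. Leave other adjustments to sensitivity analyses.

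The cost is SAP wording. ADL takes one degree of freedom, about 0.1 point of power if it proves irrelevant; the listed factors take a few more. The high/low factor needs no new data. If the Barthel score is used instead, the plan should state when the baseline value is taken.

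### Extra covariates enter the primary and secondary models by their observed relation to outcome and observed imbalance, from an open list, so the primary estimate is not uniquely defined in advance

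*Combined protocol and SAP*

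**What the plan says.** Under Data Analysis, Hypothesis #1, the mixed model for the follow-up depression scores is "adjusted for site and baseline scores as fixed effects", and the definition of its terms describes a model "with covariates for baseline depression and time since discharge". Those terms are fixed in advance.

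The text after the reduced model then widens it: "In order to control for possible chance sample imbalances resulting from randomization, the model will include covariates for baseline prognostic factors". The factors are given only as examples: "e.g., discharge from hospital, community living center, or rehabilitation facility; caregivers' relationship to Veteran" and "number of previous strokes among Veterans, etc". A factor qualifies if it is "deemed to have significant relationships with response and groupwise imbalances". This applies to the model that yields the primary contrast β5: "Of primary interest is the estimated within-site intervention effect at approximately 11 weeks after baseline data collection, controlling for baseline covariates and stratifying by site".

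The Hypotheses #3 text repeats the rule for the count outcomes: "all models will include covariates for prognostic factors deemed to have significant relationships with response and significant groupwise imbalances". The Hypothesis #2 outcomes and the Barthel Index are to be analysed by the Hypothesis #1 plan, so they inherit the rule.

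The plan does not say which test or cut-off decides either condition, in what order candidates are examined, or who decides. Nor does it keep a model without the extra factors as primary. The Randomization section balances on depressed or not, high or low ADL, and site. ADL level is not a fixed term in the primary model.

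**The concern.** Whether a factor enters depends on two features of the realized data: its association with the outcome and its difference between groups. With an open list and no criteria, two competent analysts could follow the text faithfully and report different values of β5 and different p-values from one dataset.

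Two things are at stake. The first is the error rate: if the list and criteria can be settled after results are visible, the nominal 5% is no longer assured. The second is precision. In a randomized trial the useful reason to adjust is prognostic value, which can be judged beforehand. Also requiring an observed imbalance means that most prognostic factors are left out in most realizations.

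**Working it through.** **Inputs.** From Rationale for Study Sample Size: difference 3.5, SD 8.2, 84 evaluable per group, 80% power, 5% level. Sidedness is not stated; two-sided is assumed. The plan gives no figure for the covariate rule, so its effect was simulated.

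**The plan's own figure.** Power = Φ[(3.5/8.2)·√(84/2) − 1.96] = Φ(2.766 − 1.960) = Φ(0.806) = 79.0%, against the stated 80%. It is reproduced to within about a point. Exactly 80% needs 87 per group, so there is little slack.

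**How often the rule acts.** Suppose both conditions are tested at 0.05. A factor certain to pass the outcome test still passes the imbalance test only 5% of the time. With 3 such factors, at least one enters with probability 1 − 0.95³ = 14.3%; with 10, 1 − 0.95¹⁰ = 40.1%. Weaker factors sometimes miss the outcome test, so simulated rates are lower: 9–14% with 3 candidates and 30–32% with 10. When a factor does enter, the estimate moves by 0.7–0.9 CES-D points on average (0.66/3.5 = 19% to 0.90/3.5 = 26% of the planned effect). Significance at 0.05 changes in 7–15% of those trials.

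**Type I error.** All runs use 84 per arm and simplify to one 11-week comparison. Set A: 4,000 trials, 6 candidates (3 prognostic, 15% of residual variance) or 10 (5 prognostic, 20%). Set B: 6,000 trials, 3 or 10 independent normal candidates, each with a coefficient of 0.2–0.3 outcome SD, and a baseline coefficient of 0.5. Further runs varied these settings. Simulation error is about 0.3 points.

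| Use of the rule, no true effect | Type I error |
|---|---|
| Mechanical, both tests at 0.05, set A | 4.5%, 4.8% |
| Mechanical, set B | 3.8–4.8% |
| Mechanical, further run | 4.5–5.5% |
| Smallest p over five readings, set B, 3 candidates | 7.0–7.4% |
| Same, set B, 10 candidates | 9.9% (5.6% with no extras) |
| Smallest p over five readings, further run | 5.6–7.7% |
| Most favourable single-covariate model, set A | 7.2% (6), 8.6% (10) |
| Same, only candidates meeting both conditions at 0.05, further run | 6.2% (6), 5.5% (10); 5.8%, 4.9% with no extras |
| Fixed list always included, sets A and B | 4.5–5.7% |

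In set B the five readings are: no extras; both conditions at 0.05; outcome relation only; imbalance only; outcome relation with imbalance at p < 0.20.

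**Precision.** If always-included factors explain a share R² of residual variance, power = Φ[2.766/√(1 − R²) − 1.96].

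- R² = 0.02: Φ(0.834) = 79.8%
- R² = 0.05: Φ(0.878) = 81.0%
- R² = 0.15: Φ(1.040) = 85.1%
- R² = 0.20: Φ(1.133) = 87.1%

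Against 79.0%, the gains are 0.8, 2.0, 6.1 and 8.1 points. Set A agrees at the upper end: 85.3% and 87.2% with the prognostic factors always included, against 79.7% and 79.8% under the rule. Set B, which assumes stronger factors and a useful baseline score, gives 93.0–99.5% against 88.4–90.1%. If the included factors are not prognostic there is no gain: one further run gave 76.4% adjusted against 77.1% unadjusted.

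**The case against.** The strongest reply is that the core of the model is fixed, and that the rule asks for prognostic value as well as imbalance, so it is not the discredited practice of adjusting on a baseline test alone. Applied as written it holds the error rate. Most of this stands, and it limits the point in four ways.

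- A reader might infer that the rule itself inflates type I error. It does not; used mechanically it is at or slightly below nominal. The 6–10% range needs an analyst who exploits the undefined parts, and the documents describe no such conduct. If both conditions are enforced at 0.05, even picking the most favourable single covariate adds only about half a point.
- A reader might infer that selection is made on unblinded data. The documents do not say so. The only masking described is of the caller who collects the post-test assessments, but selection under coded labels is not ruled out. The outcome relation can be judged with arms pooled, and imbalance can be judged without outcomes. Coded labels would still leave the list open and the criteria undefined.
- A reader might see a contradiction between the two statements of the rule, because only the second repeats the word significant before imbalances. In the first, the word can govern both conditions, so little rests on this.
- The power gain rests on an assumed R². The prognostic value of the three named factors for caregiver depression is not given.

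What the reply does not meet is that the extra terms enter the same model that supplies β5, through a list and criteria that nobody could apply uniquely.

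**Conclusion.** The point holds as a defect of specification. The covariate set for the primary model, and for the secondary models that inherit the rule, is settled by realized data under criteria that are not stated, so the primary p-value is not unique in advance. Mechanical use keeps type I error at about 4–5.5%. Discretion can raise it to roughly 6–10%, depending on the number of candidates and the readings allowed. The precision forgone is about 0–2 power points at R² of 2–5% and about 5–8 points at 15–20%. These sizes rest on assumed candidate numbers, covariate strengths and test thresholds, and on a single-visit simplification of the mixed model. The estimator remains usable, and the documents give no ground for saying that the trial's result would be biased.

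**What to change.** Delete the selection rule in both places (Hypothesis #1 and Hypotheses #3). Replace it with a closed list, fixed in advance and always included whatever the p-values or balance:

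- the terms already fixed for each model (for the primary model: site, baseline depression, time since discharge);
- high or low ADL, because randomization balances on it and at present it can enter only through the rule being deleted;
- the three factors already named: discharge facility type, caregiver relationship, number of previous strokes.

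The list must add to the fixed terms. Closing it at the three named factors alone would shut out ADL and, read literally, the fixed terms as well. State the coding, and collapse sparse categories in advance, above all in the count models. The Hypotheses #3 text also says that no baseline covariates enter the count models, presumably meaning baseline values of the counts; reword it so that it does not clash with the list. Any imbalance-driven adjustment becomes a labelled sensitivity analysis.

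The cost is wording and a few degrees of freedom. As an illustration: ADL 1, three facility types 2, previous strokes as a number 1, and relationship in two groups (an assumption) 1, giving 5 in all against 168 analysed. If the named factors are only weakly prognostic there is little or no power gain, but the primary analysis is then uniquely defined.
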